10.2. Laboratory Evaluations

At each visit, clinical laboratory tests will be conducted at the study’s central laboratory. Clinical laboratory tests will include:

- Hematology: complete blood count with differential, platelet count

This document is confidential.

SAP Version: 3.0 (15JUL2021)
Controlled Document ID: **3903A.01**, Effective Date 29-Oct-2018
Filing requirements: TMF

Page 41 of 52

Statistical Analysis PlanSponsor: Avalyn Pharma, Inc.; Protocol No.: AP01-002

- Serum Biochemistry: bilirubin, alkaline phosphatase, sodium, potassium, chloride, bicarbonate, urea, creatinine, total protein, albumin, glucose, ALT, AST
- Urinalysis: pH, specific gravity, presence/absence of protein, glucose, blood
- Biomarkers: MMP3, CCL18, CXCL13, CA19-9, CA-125

Clinical laboratory results will be summarized using Standard International System of Units (SI) units. Laboratory measurements will be summarized for all protocol scheduled time points. Descriptive statistics (n, mean, SD, median, min and max) will be presented for all clinical chemistry, hematology, urinalysis (continuous) and biomarker (CA19-9 and CA125) laboratory parameters at each scheduled visit. Change from baseline at each scheduled post-Baseline visit will also be presented.

Patient counts and percentages of patient for each category of each urinalysis (categorical) parameters will be summarized at each scheduled visit.

Shift tables (i.e., low-normal-high at Baseline versus low-normal-high at each post-Baseline visit in a 3-by-3 contingency table) will be provided for hematology, clinical chemistry, urinalysis and biomarker to assess changes from baseline in laboratory values by visit.

A listing for all laboratory results for each laboratory category (hematology, serum biochemistry, urinalysis and biomarkers) and a listing of treatment-emergent abnormal values will be presented.

10.3. Vital Signs

Vital sign measurements including systolic blood pressure, diastolic blood pressure, pulse rate, respiration rate, and body temperature at each scheduled time and changes from baseline in vital sign measurements will be summarized with descriptive statistics at each scheduled time point by treatment group. Temperature will be displayed in Celsius.

Body height will be measured at Screening only and will be summarized by treatment group. Weight will be measured at Screening and Week 12, 24, 48 and 72 visits and, along with changes from baseline, will be summarized with descriptive statistics at each scheduled time point by treatment group. Weight will be displayed in kilograms; height will be displayed in centimeters.

Body mass index (BMI) will be derived from the weight (at Week 12, 24, 48 and 72) and height (at Screening) along with changes from baseline, will be summarized with descriptive statistics at each schedule timepoint by treatment group. BMI will be displayed in kilograms per meter squared.

All vital signs data will be presented in a listing.

10.4. Physical Examination

A complete PE will be performed at the Screening and Baseline visits. This will include physical examination of the following body areas and systems: examination of general appearance, skin, head, neck (including thyroid), eyes, ears, nose, throat, heart, lungs, abdomen, lymph nodes, extremities, and nervous system.

A modified PE of the lungs and CV body systems will be performed at each subsequent visit.

This document is confidential.

SAP Version: 3.0 (15JUL2021)
Controlled Document ID: **3903A.01**, Effective Date 29-Oct-2018
Filing requirements: TMF

Page 42 of 52

Statistical Analysis PlanSponsor: Avalyn Pharma, Inc.; Protocol No.: AP01-002

A complete or modified physical exam is optional at unscheduled visits, per the investigator's discretion.

The physical examination data will be presented in a listing.

10.5. Saturated Oxygen (SaO₂) Assessment

Saturated Oxygen (SaO₂) assessments will be performed at Screening, Baseline (Pre-Dose and Post-Dose) and at all post-Baseline Visits (Week 4, 8, 12, 16, 20, 24, 36, 48, 60, 72 and Follow-Up). The SaO₂ % result will be captured and an indication will be noted if a patient received supplemental oxygen and, if so, the number of liters per minute. For Pre-Dose at Baseline, patients with SaO₂ < 90% will be administered supplemental oxygen until the SaO₂ reaches 93% prior to dosing.

The following statistics for SaO₂ will be calculated and summarized by treatment group and displayed in a table:

- Number and percentage of patients in each treatment group that had a SaO₂ result at screening, Baseline (pre-dose) and at each post-Baseline time point.
- Summary statistics of SaO₂ at screening, Baseline (pre-dose) and at each post-Baseline time point (Week 4, 8, 12, 16, 20, 24, 36, 48, 60, 72 and Follow-Up)
- Summary statistics of SaO₂ reflecting the absolute change from Baseline (pre-dose) to each post-Baseline time point (Week 4, 8, 12, 16, 20, 24, 36, 48, 60, 72 and Follow-Up).

The following plot will be produced for SaO₂:

- Mean SaO₂ Change from pre-dose Baseline (±SD) vs. Visit Week (Week 4, 8, 12, 16, 20, 24, 36, 48, 60, 72 and Follow-Up) with lines for each treatment group.

All SaO₂ data will be presented in a listing.

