#### **Figure 1: Part A Study Schema**

**PART A – Patients are randomized at Visit 2 to either 50 mg given once daily or 100 mg AP01 given twice daily**

#### **Figure 2: Part B Study Schema**

**PART B – Patients continue randomized treatment regimen of either 50 mg once daily or 100 mg AP01 twice daily**

In Part A, eligible patients at least 40 years of age with a confident clinical and radiographic diagnosis of IPF according to pre-specified criteria,  $40 \leq \%FVC \leq 90$ ,  $FEV_1/FVC$  ratio  $\geq 70\%$  and  $30 \leq \%DL_{CO} \leq 90$  will be randomized with equal probability to receive AP01 50 mg once daily or 100 mg twice daily for 24 weeks. Other than brief periods of medically appropriate treatment for acute IPF exacerbation, patients will not receive any other therapy for the treatment of IPF during Part A. If in the opinion of the investigator, a patient is in need of treatment with oral pirfenidone or nintedanib during Part A, the patient should be discontinued from the study and return to the clinic for their Early Termination visit. Supplemental oxygen will be allowed during the entire study.

Avalyn Pharma, Inc.  
AP01-002

Protocol v2.1  

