6.2.3. Baseline and Change from Baseline

Baseline is defined as the last non-missing measurement prior to or on the first dose of study drug.

Change from baseline = (post-baseline value – baseline value). For the purpose of tabulations, the unscheduled post-baseline values generally will be excluded.

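### The SaO2 change table and plot in SAP 10.5 ignore the recorded oxygen flag and flow, so worsening that leads to oxygen can appear as stable saturation

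*SAP*

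**What the plan says.** SAP 10.5 has SaO2 measured at Screening, before and after dosing at Baseline, and at every later visit through Follow-up. With the result, "an indication will be noted if a patient received supplemental oxygen and, if so, the number of liters per minute".

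The planned outputs are:

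- a table by treatment group that includes "Summary statistics of SaO₂ reflecting the absolute change from Baseline (pre-dose) to each post-Baseline time point";
- a plot, "Mean SaO₂ Change from pre-dose Baseline (±SD) vs. Visit Week", with one line per arm;
- a listing: "All SaO₂ data will be presented in a listing".

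The tables and plot contain no split, exclusion or adjustment by oxygen status or flow, and no SaO2 output counts patients who start oxygen or change flow.

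Protocol 4.1 states: "Supplemental oxygen will be allowed during the entire study". Neither document requires SaO2 to be read on room air.

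On Day 1, before dosing, "patients with SaO₂ < 90% will be administered supplemental oxygen until the SaO₂ reaches 93% prior to dosing" (SAP 10.5; Protocol 6.2.2 has the same rule). SAP 10.5 calls the baseline the pre-dose value but does not say which value applies when oxygen was given. The general rule in SAP 6.2.3 is: "Baseline is defined as the last non-missing measurement prior to or on the first dose of study drug".

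SAP 6.6 lists supplemental oxygen use (yes/no) among its baseline subgroups. Those subgroups apply to the primary efficacy endpoint and to a general adverse-event and tolerability summary, not to SaO2.

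**The concern.** A saturation reading taken on oxygen reflects the oxygen given as well as the patient's gas exchange. The change between a room-air reading and an on-oxygen reading therefore mixes disease course with treatment. The population is progressive: eligibility allows FVC down to 40% and DLCO down to 30% of predicted, no criterion limits oxygen use, and treatment runs to Week 72. Some patients can be expected to start oxygen or need more of it.

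At stake is what a reader takes from the SaO2 table and plot. A flat line could mean that saturation held, or that it fell and oxygen restored it. The study is open-label, and SAP 6.1 evaluates dose response partly by comparing safety across regimens. If oxygen uptake differed by arm, the two plotted lines would not be comparable. The Day 1 rule raises a related question: for a patient given oxygen before dosing, the baseline itself may be an on-oxygen value.

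**Working it through.** The plan states no SaO2 mean, SD, sample-size figure or oxygen-uptake rate, so there is no figure to reproduce. The 90% and 93% thresholds come from SAP 10.5. Shares of patients, gains and room-air values below are assumptions.

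**1. Masking, mean over an arm.** Overstatement of mean change = share with new or increased oxygen × SaO2 gain from it.

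| Share (assumed) | Gain in points (assumed) | Overstatement in points |
|---|---|---|
| 10% | 3 | 0.10 × 3 = 0.3 |
| 20% | 4 | 0.20 × 4 = 0.8 |
| 30% | 6 | 0.30 × 6 = 1.8 |

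**2. Masking, patient by patient.** Suppose a patient reads 93% on room air at Baseline, falls to 85–89% on room air, starts oxygen and is read at 93%. The planned table records 93 − 93 = 0. The room-air change is 89 − 93 = −4 to 85 − 93 = −8. If the rest of the arm is unchanged, the planned mean change is 0.0 in every row below.

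| Share of arm (assumed) | Room-air mean change in points |
|---|---|
| 5% | −0.2 to −0.4 |
| 10% | −0.4 to −0.8 |
| 20% | −0.8 to −1.6 |
| 30% | −1.2 to −2.4 |

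**3. The reverse direction.** Suppose the baseline value is 93% on oxygen, the same patient's room-air level is 85–89%, and a later reading is on room air. The table shows −4 to −8 points with no true change. At 5 to 20% of an arm, that is a false mean fall of 0.05 × 4 = 0.2 to 0.20 × 8 = 1.6 points.

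**4. Which Day 1 value is baseline.** A reading below 90% triggers oxygen to 93%, and both readings precede dosing. If both are entered, the SAP 6.2.3 rule selects the later, on-oxygen value, which exceeds the triggering one by more than 93 − 90 = 3 points. If only the triggering reading is entered, baseline is the uncorrected value. Protocol Table 5 and SAP Table 3 each show a single pre-dose SaO2 row, and the documents do not say which reading fills it.

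**5. Would restricting to same-flow readings solve it?** Take the 20% row of step 2. Dropping those patients leaves the 80% with no change, so the restricted mean is again 0.0 while the room-air mean over the whole arm is −0.8 to −1.6. Restriction alone reproduces the masking.

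**The case against.** The strongest case on the other side concerns weight. SaO2 is not among the safety endpoints in SAP 4.4, nor among the measures that the opening of SAP section 10 gives as the basis for assessing safety. No SaO2 model or between-arm contrast is planned. Deterioration has other routes to the reader: DLCO is summarised by arm and modelled, FVC is the primary efficacy analysis, and a condition that worsens on study is recorded as an adverse event. All of this stands, and it limits the point to the reading of one supportive table and plot.

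Three stronger readings are tempting, and the documents do not support them.

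- A reader might infer that worsening is recorded as stable saturation. It is not: the flag and flow are captured and listed. It can only appear stable in the table and plot.
- A reader might infer that every patient given oxygen on Day 1 carries an inflated baseline. That holds only if the post-oxygen value is entered, which the documents do not establish.
- A reader might infer that the bias always favours the drug or one arm. Steps 2 and 3 of the working run in opposite directions, and the net sign is unknown.

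Two defences of the plan do not close the gap. The SAP 6.6 subgroup is a baseline grouping that does not cover SaO2 and cannot capture oxygen started later. The concomitant-therapy summary in SAP 7.6 counts a patient once per drug class, without visit or flow. The listing holds the information, but a reader would have to rebuild the comparison by hand.

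**Conclusion.** The point holds as a cheap improvement. As written, SAP 10.5 can show stable saturation in patients who worsened and started oxygen, and can show a false fall where an on-oxygen baseline precedes a room-air reading. Nothing elsewhere in the protocol or SAP prevents either.

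The size cannot be derived from the documents. The range of 0.3 to 1.8 points rests entirely on the assumed 10 to 30% uptake and 3 to 6 point gain. It describes masking alone and is not netted against the reverse effect. The baseline part is conditional on both Day 1 readings being entered.

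The documents do not support the inference that the trial's safety conclusions or the FVC result are compromised: SaO2 is descriptive and supportive, and those analyses do not use it. The 90%/93% oxygen rule itself is not questioned, only which reading is analysed and how.

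**What to change.** Amend SAP 10.5 as follows.

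1. Define the SaO2 baseline as the first Day 1 pre-dose reading, before any protocol oxygen, and carry its oxygen status with it. State that this overrides the general rule in SAP 6.2.3 for SaO2.
2. Keep the all-readings summary. Add SaO2 change split by oxygen status relative to baseline: same status and flow; new or increased; reduced or stopped. Do not replace the all-readings summary with same-flow readings alone. That would condition on a post-randomisation event and drop the patients who worsened (step 5 of the working).
3. Tabulate, by arm and visit, the number and percentage of patients with new, increased, reduced or stopped oxygen. New or increased oxygen is then visible as worsening, and no patient disappears between tables.

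The cost is SAP wording and programming, since the oxygen flag and flow are already collected. It assumes that they describe the patient's oxygen at the time of the reading, which should be confirmed against the case report form. The downside is extra tables and small numbers in some cells.

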10.6. Pre and Post-Dose Spirometry at Baseline

At the Baseline visit, the first dose of study drug will be administered at the clinic; post-dose Spirometry will be performed and the post-dose spirometry FEV₁ results will be compared with the pre-dose FEV₁ results. Patients that have a ≥ 15% drop in FEV₁ % predicted in their pre-dose to post-dose readings and who are symptomatic will be required to use 1 - 2 puffs (90 - 100 µg) of salbutamol prior to dosing throughout the study unless these patients are currently taking a long-acting beta-2-agonist therapy.

If based on the investigator's opinion, the patient had tolerability issues during the first dose administration, a second dose, at least 4 hours later, will also be observed at the Baseline visit. For the second dose, a second pre-dose spirometry and post-dose spirometry will be performed. In addition, pre- and post-dose SaO₂ will also be recorded for the second dose.

For the first dose, the following statistics for pre- and post-dose FEV₁ results will be calculated and summarized by treatment group and displayed in a table:

- Number and percentage of patients in each treatment group that had an FEV₁ result at Baseline (pre-dose) and post-dose at Baseline
- Summary statistics of FEV₁ at Baseline (pre-dose) and at Baseline (post-Baseline)
- Summary statistics of FEV₁ reflecting the absolute change from Baseline (pre-dose) to Baseline (post-dose).

This document is confidential.

Statistical Analysis PlanSponsor: Avalyn Pharma, Inc.; Protocol No.: AP01-002

- Number and percent of patients who had a $\geq 15\%$ drop in FEV₁ % predicted in their pre-dose and post-dose reading at Baseline.
 - For those with this drop, the number and percent that were symptomatic:
 - ◆ For those who were symptomatic, the number and percent that were discontinued due to intolerance or were given salbutamol and re-dosed at clinic,
 - For those who were re-dosed, summary statistics of their FEV₁ % predicted drop after that second dose and the number and percent who discontinued study.

All Baseline Pre- and Post-dose (first dose and second dose, if needed) spirometry data will be presented in a listing.

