12 OCT 2020

### **3. STUDY ENDPOINTS**

#### **3.1. Safety Outcome Measures**

- Treatment-emergent AEs
- Change from pre-dose to post-dose FEV1 after initial dose
- Treatment-emergent deaths
- Treatment-emergent changes in clinical laboratory findings
- Changes in vital signs

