12 OCT 2020

The initial dose of drug will be administered in the clinic to confirm airway tolerance. If based on the investigator's opinion, the patient had tolerability issues during the first dose administration, a second dose, at least 4 hours later, will also be observed. Patients who experience cough that limits their ability to complete dosing will be given 1 - 2 puffs (90 - 100 micrograms ( $\mu\text{g}$ )) of salbutamol in order to complete the in-clinic dose. These patients, as well as patients with a history of asthma or smoking history of 20 pack years or greater, or patients that have a  $\geq 15\%$  drop in FEV1 percent predicted in their pre-dose and post-dose readings will be required to use 1 - 2 puffs (90 - 100  $\mu\text{g}$ ) of salbutamol prior to dosing throughout the study unless these patients are currently taking a long-acting beta-2-agonist therapy.

Patients will have a telephone assessment at Week 1 and in-clinic assessments at Weeks 4, 8, 12, 16, 20, and 24. The Data and Safety Monitoring Board (DSMB) will perform a review of safety data from the first 20 patients after Week 4 to confirm the safety and airway tolerability of multiple dose administration. A decision to stop, continue or modify the study will be made based on this review.

Part B will collect long term safety and efficacy data for an additional 48 weeks. Patients who complete Part A through Week 24 and, in the opinion of the investigator are compliant with treatment, may select to continue the treatment to which they were randomized. The DSMB for this study met on 12 OCT 2020 to review preliminary dose comparison data. It was determined that the 100 mg twice daily dose showed a trend for amelioration of FVC loss and recommended all patients in Part B be treated with the 100 mg twice daily dose. Therefore, all patients who participate in Part B after the implementation of this amendment will be treated with the 100 mg twice daily dose. Patients participating in the AP01-005 study will continue treatment that they are receiving at Visit 12 on this study and then transition to the Rollover study upon approval of AP01-005 at their site.

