#### **6.2.2. Visit 2 - Baseline (Day 1)**

The following procedures will be conducted on Day 1 in chronological order:

- Cough Visual Analogue Scale (VAS), King's Brief Interstitial Lung Disease (KBILD) Questionnaire and Leicester Cough Questionnaire (LCQ)
- Concomitant medications since previous visit
- Record any AEs after signing informed consent
- Complete PE and vital signs

Avalyn Pharma, Inc.  
AP01-002

Protocol v2.1  

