12 OCT 2020

- HRCT (If not performed at Screening or Screening HRCT was performed more than 1 month prior to Baseline. For scheduling purposes, the Baseline HRCT may be performed up to 1 month prior to or 1 week after the Baseline visit.)
- Pre-dose Spirometry and  $D_{LCO}$
- Pre-dose  $SaO_2$ ; Patients with  $SaO_2 < 90\%$  will be administered supplemental oxygen until the  $SaO_2$  reaches 93% prior to dosing
- Blood samples for laboratory tests (Chemistry including AST and ALT, Hematology, Biomarkers (CXCL13, CCL18, MMP3, CA19-9 and CA-125)
- Urinalysis
- Urinary pregnancy test (FOCBP only)
- Confirm Inclusion/Exclusion criteria
- Randomization
- Study material training and first study drug administration; patients experiencing excessive cough or bronchospasm will be administered 1 – 2 puffs (90 - 100  $\mu$ g) of salbutamol prior to subsequent doses or during initial dosing
- Post-dose Spirometry to be performed  $\leq 10$  minutes after completion of AP01 dose (Patients with a  $\geq 15\%$  drop from pre-dose spirometry who are symptomatic will be treated as described in section 8.6.)
- Post-dose  $SaO_2$
- Study material dispensation, including salbutamol and instructions for use of salbutamol (if needed as described in Sections 8.6 and 8.7.)
- Home spirometry training and dispensation

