7.5. Drug Exposure

In this study, patients will be dosed in the clinic at Baseline to confirm tolerability for the first (and possibly second dose) and at home by the patient for all post-baseline doses. Drug exposure will be assessed as follows:

Baseline: In the Clinic

- The actual dose (mL) of AP01 for each patient will be the starting volume in the nebulizer minus the remaining volume in the nebulizer (if the full dose was not administered). If a second dose is given due to intolerance at the first dose, the actual dose will be derived in the same manner as the first dose. The number of patients who require a second dose in-clinic will be summarized and the total actual dose for each dose will be summarized by treatment group.
- The number of patients with physician-prescribed salbutamol taken prior to the dose will be summarized for each dose (first dose only if only 1 dose was received or for each dose if 2 doses are received) by treatment group with frequency counts and percentages. For patients who received salbutamol prior to dose, how many of those are because of prior toxicity for each dose and how many were added due to intolerance for the second dose will be summarized by treatment group with descriptive statistics.
- The number of patients with study drug inhalations interrupted will be summarized for each dose (first dose only if only 1 dose was received or for each dose if 2 doses are received) by treatment group with frequency counts and percentages.
- For patients with Inhalation interrupted during the second dose, the number of patients with salbutamol administered to continue dosing will be summarized by treatment group with frequency counts and percentages.
- For each patient, the time of nebulization for each dose will be derived as the study drug administration stop time minus the study drug administration start time and converted to minutes. If the study drug inhalation was interrupted, the time of interruption for each dose will be derived as the Inhalation Re-Start Time minus the Inhalation Interruption Time, converted to minutes and

This document is confidential.

SAP Version: 3.0 (15JUL2021)
Controlled Document ID: **3903A.01**, Effective Date 29-Oct-2018
Filing requirements: TMF

Page 27 of 52

Statistical Analysis PlanSponsor: Avalyn Pharma, Inc.; Protocol No.: AP01-002

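### First-dose FEV1 drops can be undercounted because patients given rescue salbutamol during the dose are pooled with everyone else in the FEV1 tables

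*SAP*

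**What the plan says.** Pre- to post-dose FEV1 change after the initial dose is a listed safety outcome (Protocol 3.1, SAP 4.4). Post-dose spirometry is also named in the primary objective (Protocol 4.1, SAP 3.1).

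Protocol 6.2.2 fixes the Day 1 sequence: "The following procedures will be conducted on Day 1 in chronological order". Pre-dose spirometry comes before the first dose. Post-dose spirometry comes after it, within 10 minutes of the dose being completed (also Protocol 7.2.1).

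Salbutamol can fall between the two readings:

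- Protocol 6.2.2: "patients experiencing excessive cough or bronchospasm will be administered" one to two puffs "of salbutamol prior to subsequent doses or during initial dosing".
- Protocol 4.1: "Patients who experience cough that limits their ability to complete dosing will be given 1 - 2 puffs" of salbutamol, so that the in-clinic dose can be completed. Protocol 8.6 and SAP 3.3 and 3.7 say the same.

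On the analysis side, SAP 10.6 sets up the comparison: "At the Baseline visit, the first dose of study drug will be administered at the clinic; post-dose Spirometry will be performed". It then summarises first-dose FEV1 change and the number of patients with a drop of at least 15%, by treatment group. Its only salbutamol row sits beneath patients who already show such a drop and are symptomatic. SAP 7.5 repeats the drop count for each dose. For rescue during a dose, SAP 7.5 has one row: "For patients with Inhalation interrupted during the second dose, the number of patients with salbutamol administered to continue dosing will be summarized". There is no matching row for the first dose.

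**The concern.** The patients who receive salbutamol partway through the first dose are those who tolerate it worst. Their post-dose FEV1 is read after a bronchodilator that the pre-dose FEV1 did not have. If the drug narrows the airways and the rescue reverses this before the reading, the patient shows no drop. That patient then never reaches the salbutamol row of SAP 10.6, because the row starts from patients with a drop. The arm mean is pulled towards no change in the same way.

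Acute airway tolerability is part of what this study is primarily meant to establish, and the number of events will be small. A count that can lose the very patients who needed rescue is hard to interpret on its own.

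**Working it through.** **Order of events in a rescued patient.** Set side by side, the sections give this sequence:

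1. Pre-dose FEV1 (Protocol 6.2.2).
2. First dose starts; cough or bronchospasm occurs; salbutamol is given (Protocol 4.1, 6.2.2, 8.6).
3. Dose is completed.
4. Post-dose FEV1 within 10 minutes of completion (Protocol 6.2.2, 7.2.1).
5. The patient enters the pooled mean and the pooled drop count (SAP 10.6, 7.5).

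Nothing in steps 4 or 5 separates this patient from one who needed no rescue.

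**The plan's own detection figure.** Protocol Table 10 (SAP Table 1) gives the chance of seeing at least one event in 50 patients. The formula is 1 − (1 − p)^50. It gives 0.395, 0.923 and 0.995 for p = 1%, 5% and 10%, matching all three cells. No such figure is given for the FEV1 outcome itself.

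**Illustration of masking.** Let p be the true rate of drops of 15% or more, and m the share hidden by salbutamol before the post-dose reading. The observable rate is p(1 − m), the expected count is 50p(1 − m), and the chance of seeing at least one is 1 − [1 − p(1 − m)]^50. The value p = 5% is the protocol's example AE rate, not an FEV1 estimate. The values of m are assumptions.

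| m | Observable rate | Expected count in 50 | Chance of at least one |
|---|---|---|---|
| 0 | 5.00% | 2.50 | 0.923 |
| 10% | 4.50% | 2.25 | 0.900 |
| 25% | 3.75% | 1.88 | 0.852 |
| 50% | 2.50% | 1.25 | 0.718 |
| 75% | 1.25% | 0.62 | 0.467 |

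**How many patients might be rescued.** Protocol 1.2.3 reports that in Phase 1 no subject's cough prevented full administration. Table 3 of the protocol shows 6 cohorts × 6 = 36 active subjects, 6 of them with IPF. With zero events in n, the exact one-sided 95% upper bound is 1 − 0.05^(1/n):

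- n = 36: 1 − 0.05^(1/36) = 8.0%, or about 4 of 50.
- n = 6 (IPF only): 1 − 0.05^(1/6) = 39%, or about 20 of 50.

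The prior data are thus compatible with no affected patients and with a sizeable minority.

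**The case against.** The strongest reply is that the event does not vanish from the report. SAP 6.6 and 10.1 plan a tolerability summary covering cough due to dosing and bronchospasm after in-clinic dosing. SAP 7.5 counts interrupted inhalations for each dose, including the first, and salbutamol taken before each dose. Concomitant medications are summarised by class, and all Day 1 spirometry is listed. This stands: a reader might infer that rescued patients go unrecorded, and the documents do not support that. But none of these items ties rescue during the first dose to the FEV1 result, so none corrects the FEV1 tables. A second observed dose does not settle it either. Under Protocol 8.6, patients rescued for cough use salbutamol before their second dose unless they take a long-acting beta-2-agonist.

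The next reply is that rescue is mostly for cough, and cough is not an FEV1 drop. This also stands in part. Only Protocol 6.2.2 names bronchospasm as a reason; 4.1 and 8.6 name cough alone. Rescue for cough masks a drop only in a patient who also has one.

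Third, Phase 1 gives little sign of the problem. Its one drop above 15% (17%, after 100 mg) was in a volunteer and was asymptomatic, so it offers no example of a drop that rescue would have hidden.

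Two further inferences are tempting and unsupported:

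- *A larger bias at 100 mg.* Table 3 shows 11–15 minutes of nebulisation at 100 mg in IPF patients and 4–8 minutes at 50 mg, but the latter were healthy volunteers. No document links rescue to nebulisation time. The idea is plausible, not shown.
- *The same distortion in patients who take salbutamol before the first dose.* The documents do not say whether that salbutamol comes before or after the pre-dose spirometry. If before, both readings follow a bronchodilator.

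**Conclusion.** The point holds as a possible undercount in the FEV1 tables. The timing of rescue and readings, and the pooling, are both in the text. The direction is towards too few drops and too small a mean fall. This assumes that salbutamol given during the dose has some effect by the post-dose reading, and that some rescued patients would otherwise have shown a drop.

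The size cannot be computed. The documents give neither the share of patients rescued nor the share of drops hidden, and the true effect may be nil. A reader might take the illustration as an estimate; it only shows that with about 2.5 expected events per arm at a 5% rate, losing one or two would matter. The documents do not support saying that drops will be missed, or that the dose comparison is biased.

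The study is descriptive, with no hypothesis test on this outcome, so the consequence is a tolerability figure that may look better than it should. That is worth correcting because the outcome belongs to the primary objective and the correction is cheap.

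**What to change.** Change the analysis only; patient handling stays as it is.

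1. In SAP 10.6, report first-dose FEV1 change and the count of drops of 15% or more by arm for all patients, and separately by whether a bronchodilator was given between the pre-dose and post-dose readings.
2. Add a supportive combined count by arm: a drop of 15% or more, or salbutamol given during the first dose before the post-dose reading, or first dose not completed. Label it a tolerability measure, not bronchoconstriction, since it includes rescue for cough alone.
3. In SAP 7.5, extend the row on salbutamol given to continue dosing to the first dose. First confirm that the eCRF captures when that salbutamol was given; the documents do not show this.

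Separately, Protocol 4.1 and 8.6 must be reconciled on patients with an asthma history or at least 20 pack-years. Section 4.1 requires salbutamol before dosing throughout the study, while 8.6 requires it before the second dose and for dosing throughout the study. Whether these patients use it before the first dose is therefore unclear, and SAP 3.3 and 3.7 carry the same difference.

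The cost is a few more table rows and a tolerability figure that may look less favourable.
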